A key purpose of the proposed study is to examine what types of tolerability concerns, if any, emerge and the timing of those events, in order to better assess how the use of this combination of tobacco cessation medicines can be most effectively delivered and monitored.

C. Detailed study protocol

Participants (n=40) will be recruited via Facebook ads contextually tagged to appear only to adults in the Madison, WI, area who have "liked" or posted about smoking. Those who click the ad will be taken to a Web page containing a brief description of the study and the opportunity to provide their contact information if they would like to learn more about the study.

Those persons who provide contact information will be called by study staff and provided with a more detailed description of what study participation would involve (time, risks, benefits, etc.). They will also be given an opportunity to ask questions. If they remain interested based on the description, study staff will proceed to assess inclusion/exclusion criteria for potential participants by way of a structured computer-assisted telephone interview. Participants who meet criteria will be invited to schedule an initial study visit. Those who do not meet criteria will be asked if they would like information about other smoking cessation treatment resources; if so, they will be given contact information for the Wisconsin Tobacco QuitLine.

Inclusion/Exclusion Criteria

Inclusion criteria will be: age >17 years; >=5 cigarettes/day for the previous 6 months; alveolar CO >= 6 ppm; able to read, write and speak English; planning to remain in the intervention catchment area for at least 4 months; not currently taking bupropion or varenicline; if the participant is currently using NRT, s/he agrees to use only study medication for the duration of the study; free of medical contraindications to NRT and varenicline; and, if participant is a woman of childbearing potential, using an approved method of birth control during treatment. Exclusion criteria will be: current diagnosis of/treatment for psychosis or bipolar disorder; suicidal ideation within the past 12 months; any history of suicide attempts; significant hepatic or renal impairment; history of significant allergic reactions to varenicline or any type of NRT in the past; use of any investigational drugs in the previous 30 days.

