Follow-up assessments will be conducted by telephone on a weekly basis, starting on the TQD and for four weeks thereafter (the period during which adverse events are most likely to emerge), then every two weeks for the following eight weeks. In addition to the structured assessment, study staff will also use a timeline follow-back procedure to track and smoking and noncombustible nicotine use on a daily basis during the treatment period, as these may influence treatment tolerability and efficacy assessments. Table 1 presents the study assessment schedule. In addition to the formal study assessments, participants will be able to initiate contact with study staff if they have questions/concerns regarding their treatment. Study staff will review follow-up data on a weekly basis. UW-CTRI's standing Data Safety and Monitoring Board will review overall study data after the first 5 participants have completed their first week post-quit; after the first 20 participants have reached that milestone; and at the completion of the study. [The DSMB comprises Drs. [name], [name], and [name], all of whom are independent of the pilot study.]

Analytic plan

This is an exploratory study of the tolerability and feasibility of combining varenicline with combination NRT. There is no comparison group, so no inferential statistical tests are proposed. Data regarding safety will be summarized in descriptive tables based on the adverse event organ system and reported frequency. Should any Serious Adverse Events occur, they will be captured in a narrative manner, including the PI's assessment of relatedness to study medication. Participant-reported outcomes related to treatment acceptance and impact on withdrawal will be summarized and reported tabularly with mean and standard deviation for each item. Number of participants discontinuing any medication will also be summarized across the sample.

Given that no inferential statistical tests will be performed for this single-group, open-label, descriptive pilot study, it is not appropriate to provide a statistical power analysis. The sample size of 40 was selected to provide demographic diversity in terms of gender, socioeconomic status, and smoking history variables, as well as providing robust estimates of the incidence of possible adverse events related to the combination pharmacotherapy.

Data collection and security

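### Treatment acceptance and withdrawal items are summarised only by mean and SD, which does not show how many participants gave poor ratings

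*Combined protocol and SAP*

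**What the plan says.** The Analytic plan in section C of the combined protocol and SAP describes the study's aim as follows: "This is an exploratory study of the tolerability and feasibility of combining varenicline with combination NRT". It plans no inferential tests and has no comparison group, so descriptive tables and narratives are the whole statistical output.

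For the self-reported items it says: "Participant-reported outcomes related to treatment acceptance and impact on withdrawal will be summarized", and that they will be "reported tabularly with mean and standard deviation for each item". No median, range, category count, percentage or cut-off is given for them, and the sentence does not say whether the table is by call.

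Two other summaries in the same paragraph are counts. Adverse events are tabulated by organ system and frequency. For stopping treatment: "Number of participants discontinuing any medication will also be summarized across the sample". Serious adverse events are described in narratives.

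The Assessment schedule places the withdrawal scale at Visit 1 and Calls 1 to 9, and the Combination Treatment Assessment at Calls 1 to 9. It lists these instruments by name only, without response options or item direction.

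**The concern.** A reader of a tolerability and feasibility pilot will want to know how many participants found the regimen hard to accept or had marked withdrawal, and at which call. A mean and SD describe the centre and spread of the scores. On an item with four or more ordered levels they generally do not fix the number of people at the unfavourable end, because different sets of counts share the same mean and SD.

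Participants who keep taking all three medications while rating them poorly are not counted as discontinuing, and may report no adverse event. The planned tables would not show how many they are.

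**Working it through.** **Inputs.** n = 40 is from the Analytic plan ("The sample size of 40 was selected to provide demographic diversity"). The plan derives it from no formula ("it is not appropriate to provide a statistical power analysis"), so there is no figure to reproduce. The response scale, mean and SD below are assumptions, used only to see how far a printed mean and SD pin down the counts.

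**Assumed item.** Scores 0 to 4, 40 responses, mean 1.0, SD printed as 1.2 (sample SD from 1.15 up to but not including 1.25).

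**Constraints.** Let c0 to c4 be the counts at each level.
- Sum of scores: c1 + 2·c2 + 3·c3 + 4·c4 = 40 × 1.0 = 40.
- Sum of squares: Q = c1 + 4·c2 + 9·c3 + 16·c4, with SD = √((Q − 40)/39).
- SD in the stated range gives Q from 40 + 39 × 1.3225 = 91.6 to 40 + 39 × 1.5625 = 100.9. A score and its square are both odd or both even, so Q has the same parity as the sum, and Q can only be 92, 94, 96, 98 or 100.

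**Enumeration.** There are 105 sets of counts that meet these constraints. In 13 of them the counts never rise from 0 to 4, which is the shape expected if most ratings are mild.

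| Set of counts allowed | Number scoring 3 or 4 | Number scoring 4 |
|---|---|---|
| Never rising from mild to severe | 4 to 7 (10% to 17.5%) | 1 to 3 |
| Any | 2 to 10 (5% to 25%) | 0 to 5 |

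Examples, as counts at 0/1/2/3/4:

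| Counts | Sum | Q | SD | Scoring 3 or 4 |
|---|---|---|---|---|
| 18/10/8/2/2 | 40 | 92 | √(52/39) = 1.155 | 4 |
| 21/6/6/6/1 | 40 | 100 | √(60/39) = 1.240 | 7 |
| 22/0/16/0/2 | 40 | 96 | √(56/39) = 1.198 | 2 |
| 19/11/1/9/0 | 40 | 96 | √(56/39) = 1.198 | 9 |
| 20/10/0/10/0 | 40 | 100 | √(60/39) = 1.240 | 10 |

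The third and fourth rows have the same unrounded mean and SD, so rounding is not the whole cause. Among never-rising counts rounding does contribute: at the single SD 1.155 the number scoring 3 or 4 runs from 4 to 6.

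**Dependence on the number of levels.** Over all possible sets of 40 responses:
- Five levels: 6,808 of 7,767 mean/SD pairs (88%) leave the top-category count undetermined, by up to 13 of 40.
- Four levels: 2,594 of 3,202 pairs (81%), by up to 10 of 40.
- Two or three levels: none. With three levels there are three unknown counts and three equations (n, sum, sum of squares), so n with the unrounded mean and SD gives every count.

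**The case against.** The strongest reply is that tolerability is already handled by count. The purpose paragraph that opens the study procedures says the study is to "examine what types of tolerability concerns, if any, emerge and the timing of those events". That is served by adverse event frequencies, serious-event narratives, the discontinuation count, adverse event assessment at all nine calls and three reviews by the monitoring board. The mean and SD apply only to acceptance and withdrawal, and a high withdrawal score may reflect quitting itself rather than intolerance of the drugs. This largely stands. A reader might infer that the plan cannot show whether a tolerability concern has emerged. The documents do not support that. The gap is limited to how participants rated these items.

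A reader might also take 5% to 25% as the usual size of the ambiguity. That is not supported either. A count of 10 arises only from 20/10/0/10/0, where nobody scores 2, and a count of 2 only from sets where nobody scores 3. With counts that never rise, the range is 10% to 17.5%. Sampling error at this sample size is wider: 4 of 40 has an exact 95% interval of 2.8% to 23.7%.

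Mean and SD per item is a conventional summary, nothing in the plan forbids adding frequencies, and the retained item data would allow them later. All of that is true. What remains is that the plan does not commit to counts, and a cut-off for a poor rating chosen after the data have been seen is less credible than one set beforehand.

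**Conclusion.** The point holds as a minor reporting gap. Mean and SD are the only summary stated for the acceptance and withdrawal items, and they do not show how many participants gave poor ratings. The adverse event and discontinuation counts fill the gap in part, but not for participants who stay on treatment.

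Its size depends on a response format that the documents do not give. The 10% to 17.5% range rests on an assumed 0-4 item, one assumed mean and SD, all 40 participants responding, and counts that never rise from mild to severe; 5% to 25% is the outer limit without that shape. If the items have two or three levels and the mean and SD are unrounded, there is no loss. The sample size, error rates and decision rules are unaffected.

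**What to change.** For each acceptance and withdrawal item at each call, report the number assessed and n (%) in each response category, beside the mean and SD. For the withdrawal items, show Visit 1 alongside, so that ratings already high before treatment can be recognised.

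If a single percentage with a poor rating is wanted, define the unfavourable end separately for each item, according to its direction, before the data are reviewed, and report it by call. One rule for all items, such as ever scoring in the top two categories, would not serve. The top of an acceptance item may be the favourable end. Such a rule would also ignore the Visit 1 level, grow with the number of calls completed, and hide timing.

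No new data, participants or tests are needed. The cost is longer tables; the full category tables can go in an appendix.

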At the initial study visit, potential participants will review a Powerpoint presentation with a study staff member providing detailed information about study procedures, time commitment, risks, and benefits. They will also be given the IRB-approved Informed Consent Document and allowed to take as much time as they like to read it (including the option to take it home and return at a later date). They will be given the opportunity during both the presentation and reading of the ICD to ask questions. If they choose to provide written informed consent for study participation, staff will reconfirm all inclusion/exclusion criteria, including a CO breath test. Upon reconfirmation of study eligibility, participants will be asked to complete the surveys about nicotine dependence and withdrawal, smoking history and use of noncombustible tobacco products (see Assessment schedule below).

Each participant will be evaluated medically by a study physician, based upon inclusion/exclusion criteria, baseline assessments, and physical examination, as to their fitness for combination therapy. If a participant is determined to be medically appropriate, they will be provided with the following medication regimen:

- 1. Varenicline 0.5 mg once daily for three days; followed by 0.5 mg twice daily for four days; followed by 1 mg twice daily for 11 weeks.
- 2. Transdermal Nicotine 21 mg for eight weeks (starting on the Target Quit Date); followed by transdermal nicotine 14 mg for two weeks; followed by transdermal nicotine 7 mg for two weeks (Note: for participants smoking 5-9 cigarettes/day at baseline, the regimen will be 14 mg/day for 10 weeks followed by 7 mg/day for 2 weeks).
- 3. Nicotine mini lozenges (2 mg) to be used as needed for relief of withdrawal and craving, for 12 weeks starting on the Target Quit Date. Participants will be urged to use at least four mini lozenges per day, but no more than 20 per day.

All medicines will be provided in FDA-approved dosing in the manufacturer's original packaging. Precautions related to taking the medication will be reviewed by a study physician.

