In addition to the medication regimen, all participants will be provided with a single individual smoking cessation counseling provided by [name] and trained research staff, as per the United States Public Health Service *Clinical Practice Guideline: Treating Tobacco Use and Dependence.* Participants will also be asked to access a Web-based cessation support program (www.smokefree.gov). Target Quit Date (TQD) for all participants will be set for eight days from initiation of medication to allow for normal uptitration of varenicline.

Follow-Up

All participants will be followed over the 13 week course of treatment with structured assessment of safety, tolerability, treatment adherence, smoking, use of noncombustible nicotine, and treatment satisfaction. Participants will be contacted by a study physician during the week following their TQD to perform an AE assessment. This AE assessment screens for critical indicators of potential risks related to study medication, including cardiac problems and suicide ideation. Should any questions on the screener be endorsed as unresolved symptoms, a study physician will contact the participant to further discuss the symptoms, study medication use and other related personal or medical information. All other assessments (including additional AE assessments) will be weekly telephone calls conducted by study staff utilizing structured instruments shown in the Assessment Table below (MN Withdrawal Scale, noncombustible use assessment, timeline follow-back and adverse event assessment), with reports of adverse events being followed to resolution. Attribution of AE relatedness to study treatment will be made by [name]. All AE assessments indicating unresolved symptoms which may be related to study medication will be assessed to determine any dosage adjustment (modification of dose or discontinuation of a medication.) Any Serious Adverse Events requiring reporting will be reported during mandated timeframes to the UW Health Sciences IRB and the National Cancer Institute (study sponsor).

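### Is a single count of participants stopping any medication too thin a summary of whether the triple regimen was maintained?

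*Combined protocol and SAP*

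**What the plan says.** The Analytic plan in Section C names four outputs: adverse event tables by organ system and frequency, narratives for serious events, item-level means and standard deviations for treatment acceptance and withdrawal, and a count of stopping: "Number of participants discontinuing any medication will also be summarized across the sample". It states that there is no comparison group and that no inferential tests will be done.

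Other parts of the protocol bear on the count:

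- Section B ends with a key purpose of the study: "to examine what types of tolerability concerns, if any, emerge and the timing of those events".
- Under Follow-Up, unresolved symptoms that may be related to study medication are assessed for "any dosage adjustment (modification of dose or discontinuation of a medication".
- Follow-Up also promises "structured assessment of safety, tolerability, treatment adherence, smoking, use of noncombustible nicotine, and treatment satisfaction".
- The Assessment schedule puts a Combination Treatment Assessment and an Adverse Experience Assessment at each of Calls 1 to 9. The items of the first are not shown.

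**The concern.** Only one of the four outputs says whether participants kept to the regimen, and on its natural reading it merges three products into one number. Someone who stops only the lozenge and someone who stops everything count the same. Someone whose dose is reduced is not counted at all, although Follow-Up treats dose modification and discontinuation as parallel responses to symptoms. Adherence is to be assessed but is not named among the outputs.

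The count also comes with no definition. The three products run on different clocks. Varenicline finishes before the last call, the patch steps down by design, and the lozenge is "to be used as needed for relief of withdrawal and craving, for 12 weeks starting on the Target Quit Date". Loss to follow-up is not mentioned.

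The data are meant to inform later trials. If the count were all that was reported, designers of those trials would not learn which product was dropped, when or why, and could not relate adverse event frequencies to the number of people actually taking all three medicines.

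**Working it through.** The plan gives no rate, precision target or power for this outcome, so there is no figure to reproduce. The check has three parts.

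**1. What the single count can and cannot convey.** Suppose each of the three products is stopped by a proportion p of participants (an assumption; the documents give none). The proportion stopping at least one product lies between p, if the same people stop all three, and min(1, 3p), if there is no overlap. Under independence it is 1 − (1 − p)³.

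| Assumed p per product | Lowest | Independent | Highest |
|---|---|---|---|
| 5% | 5% | 14.3% | 15% |
| 10% | 10% | 27.1% | 30% |
| 20% | 20% | 48.8% | 60% |

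So product-level rates cannot be recovered from the any-product count. Precision at n = 40 is limited in any case: an assumed 4/40 = 10% has an exact (Clopper-Pearson) 95% interval of 2.8% to 23.7%, and 12/40 = 30% has 16.6% to 46.5%. Cells split further by product, reason and call would be very small.

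Adding dose modifications does not correct the count. With 4 of 40 stopping and a further 8 having only a dose change (both assumed), stopping is still 4/40 = 10%, and stopping or modification is (4 + 8)/40 = 30%. These are two different quantities, and the first is not biased because the second is larger.

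**2. Whether the schedules make the count ambiguous.** Varenicline is given for 3 days, then 4 days, "followed by 1 mg twice daily for 11 weeks": 3 + 4 + 11 × 7 = 84 days. The quit date "will be set for eight days from initiation of medication", which is day 8 or day 9 of medication depending on how the days are counted.

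- Last varenicline day: 84 − 8 = 76, or 84 − 9 = 75, days after the quit date.
- Week 10 call: 10 × 7 = 70 days after the quit date, within the course.
- Week 12 call: 12 × 7 = 84 days after the quit date, which is 8 or 9 days after the course ends.
- Patch: 8 + 2 + 2 = 12 weeks (10 + 2 = 12 for lighter smokers), and lozenge 12 weeks, both from the quit date.

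A participant may therefore be off varenicline at the last call exactly as scheduled. But Follow-Up uses discontinuation for an adjustment made after symptoms. Reaching the scheduled end, or stepping down the patch on schedule, is not plausibly discontinuing, and an analyst with the regimen in hand would not code it so. The planned wording also summarizes across the sample, which points to all 40 as the denominator.

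**3. Whether the finer information would be available.** The instruments listed in the Follow-Up text ("MN Withdrawal Scale, noncombustible use assessment, timeline follow-back and adverse event assessment") include none for use of study medication. That same sentence refers the reader to the assessment table, however, and the table adds the Combination Treatment Assessment at all nine calls. Since adherence is said to be assessed, this is the likely place for use items. If they are there, some may fall under the planned item-level summaries, and the call at which a change was reported gives its approximate timing.

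**The case for a change.** The strongest reply is that in a study without tests the named summaries are the result, so leaving out dose modification and product-level stopping leaves out part of the answer to the study's own question. Serious-event narratives would give reasons for stopping only when the event was serious. An item mean and standard deviation would not show who stopped what, when or why. The addition would also be cheap: a sentence, a few tables and a listing.

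Part of this stands. No section names a summary of dose modification, and none promises a split by product, time or reason. Saying so would make the plan more informative.

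The rest is weaker. The sentence can also be read as covering discontinuation of whichever medication, and nothing in it rules out a by-product table. The timing named in Section B is that of tolerability concerns, which bears most directly on the adverse event tables and not on discontinuation. Whether adherence would go unreported cannot be known without the instrument. A stricter specification would also bring its own difficulty, because discontinuation and dose modification of an as-needed lozenge have no obvious definition and would have to be invented.

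**Conclusion.** No change to the plan is needed. The Analytic plan leaves detail unstated that analysts can be expected to supply. Followed as written, it yields a correct descriptive count in an open-label pilot of 40, alongside adverse event tables, serious-event narratives and review of overall study data by the monitoring board. No estimate is distorted and no test or decision rule depends on the count.

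The size of any loss of information is unknown, because every stopping, modification or loss-to-follow-up count used above is an assumption.

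The conclusion rests on two assumptions: that the analysts will present stopping by product when they have it, and that the Combination Treatment Assessment or the adverse event record identifies the product. If the second failed, the gap would lie in data collection, which the documents do not show, and rewording the Analytic plan alone would not close it. Naming dose modification beside discontinuation when the tables are laid out would be good practice, and needs no amendment.
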